6.2 Units and Precision

No intermediate rounding is performed in SDTM datasets; only final values for TFLs are rounded as follows. Immunogenicity titers are reported with one decimal place or two significant digits (e.g., 0.032, 18.0). Ratios of GMTs are presented with two decimal places.

Vital sign data are reported using standard international units. Vital signs variables including derivations thereof are reported to the same precision as the source data. Parameters derived directly from source data (e.g., minimum, maximum) or first-order statistics (e.g., mean) are reported and analyzed with the same precision as the source data. Second-order statistics (e.g., SD) are reported with one more significant digit than the source data. Percentages are reported to one decimal place.

6.3 Derived Variables

This section provides definitions of the derived variables. In some cases, the definitions are provided in the relevant sections as noted.

AE, causing study discontinuation, is defined as a Yes response to the corresponding question on the AE eCRF.

AE, medically attended (MAAE), is defined as a Yes response to the corresponding question on the AE eCRF.

AE, **related**, is defined as one that is "probably" or "possibly" related to IP per investigator assessment on the eCRF. If the relationship is missing for one or more occurrences of an AE for a given participant, the closest relationship of the remaining occurrences of the AE for that participant is used; if the relationship is missing for the only occurrence of an AE for a given participant, then that event is assumed to be related in order to be conservative.

AE, resulting in death, is defined as a Yes response to the corresponding question on the AE eCRF and/or a fatal outcome.

AE, serious, is defined per the derived eCRF field for AE seriousness, based on the individual criteria that make an AE qualify as serious (results in death, is life-threatening, requires inpatient hospitalization or prolongation of existing hospitalization, results in persistent or significant disability/incapacity, or is a congenital anomaly or birth defect, or any event that may require medical or surgical intervention to prevent one of these outcomes).

AESI is defined in this study as new onset or worsening arthralgia that is medically attended, as noted by an AE having a Yes response to the corresponding AESI question on the AE eCRF.

AE, severity, is graded Grade 1 (mild) to Grade 4 (potentially life-threatening) as described in Section 5.9. If the severity is missing for one or more occurrences of an AE for a given participant, the maximum severity of the remaining occurrences of the AE for that participant is used; if the severity is missing for the only occurrence of an AE for a given participant, then that event is assumed to be severe in order to be conservative.

AEs, solicited, are defined as those collected in the electronic e-diary or paper diary. Solicited AEs include local (i.e., pain, redness, and swelling) and systemic reactions (i.e., fever, chills, fatigue, headache, myalgia, arthralgia, and nausea). *Solicited AEs were to be entered on Day 1 through Day 8; solicited AEs starting on Day 9 or later will be excluded from tabulations, with the exceptions of AESI and SAEs.*

The denominator for solicited AE tables comprises only those participants with at least one diary observation (i.e., any non-missing values but excluding "Not done/unknown"), at least one diary observation for a given symptom, or at least one diary observation for a given day, as applicable. *Note that an elevated in-clinic temperature assessment as part of 30-min post-vaccination vital signs does not count as a solicited AE, as vital signs data are summarized separately.*

AE, treatment-emergent. AE collection begins at Day 1 (baseline), the day of IP administration. AEs occurring after a participant has given informed consent, but before vaccination, are excluded from summaries. Only treatment-emergent AEs are summarized.

AEs, unsolicited, are defined as those AEs not listed in the e-diary or paper diary but collected in the EDC. Unsolicited AEs were to be collected though Day 29 unless they were SAEs, AESI, or MAAEs; unsolicited AEs starting on Day 30 or later that are not SAEs, AESI, or MAAEs are excluded from tabulations.

Age at screening visit is automatically calculated by EDC based on date of birth versus date of informed consent. Age at baseline (Day 1) is be summarized in all outputs.

Age group strata are defined as ages 12 to <18, 18 to <46, and 46 to <65 as randomized. Note that, if a participant is randomized into a stratum and their age is later corrected such that they should have been placed into a different age stratum, the participant is analyzed according to the corrected age stratum for immunogenicity analyses.

Analysis visits are defined in Section 5.5.

Analysis populations are defined in Section 5.3.

Baseline is defined in Section 5.6. Change from baseline is defined as (value at post-baseline assessment – value at baseline).

Baseline seropositive rate is defined as the percentage of participants with anti-CHIKV human SNA assay titer \geq LLOQ.

Body mass index at screening visit is automatically calculated by EDC as a participant's weight in kg divided by height in m^2 .

Anti-chikungunya virus (anti-CHIKV) human SNA assay NT₈₀ (80% neutralizing titer) is defined as the dilution factor that corresponds to an 80% reduction of luciferase activity compared to virus-only control. Anti-CHIKV SNA titer values below LLOQ are replaced by LLOQ/2 in the immunogenicity analyses including GMT and GMFI. For the 4-fold rise over Day 1 (baseline), values below the LLOQ are replaced with the LLOQ.

Completion of study for an individual participant is defined as completion of the Day 183 EOS and any required safety follow-up (i.e., a disposition status of completed).

Early discontinuation for an individual participant is defined as completion of the Early Discontinuation/ Withdrawal Visit (i.e., a disposition status other than completed).

Enrolled/randomized is defined as receipt of a randomization number assignment within the EDC system.

Lot number. Randomization code lot letters correspond to lot numbers as follows:

- Lot $104 \rightarrow A$
- Lot $105 \rightarrow B$
- Lot $106 \rightarrow C$

Medical history items entered on the medical history eCRF are considered to predate the study regardless of onset date.

Medication, concomitant, is defined as one taken after start of IP administration on Day 1 (baseline) through the end of study. For analysis purposes, any medication which is ongoing or with a stop date that is on or after the start date of IP administration is categorized as a concomitant medication. Partial or missing concomitant medication start and/or end date are imputed according to Section 6.5.2.

Medication, prior, is defined as one with a stop date within 30 days prior to the screening visit (90 days for blood products) through the start of IP administration on Day 1 (baseline).

Protocol deviations are defined by inclusion in the EDC protocol deviation module (participant-level only, not site-level), including monitor-identified deviations as well as Sponsor- and EDC system-identified programmatic deviations. Protocol deviations are classified by category and type (important/not important).

Randomized participant not meeting entry criteria is defined using the protocol deviation dataset and not just the inclusion exclusion criteria dataset, because a project team decision was made to keep the inclusion exclusion criteria as entered at the time of randomization even if the participant was later found to have violated entry criteria. These violations are recorded as protocol deviations.

Rounding of values is described in Section 6.2.

Seroresponse rate is defined as the percentage of participants who achieve an anti-CHIKV SNA titer

Seroresponse rate, composite, is analyzed at Day 22 if the baseline seropositive (anti-CHIKV SNA titer \geq LLOQ) rate is \geq 10%. The composite seroresponse rate endpoint is defined as follows:

- For participants seronegative at baseline (anti-CHIKV SNA titer <LLOQ), a seroresponse is defined as an anti-CHIKV SNA titer at Day 22.
- For participants seropositive at baseline (anti-CHIKV SNA titer ≥LLOQ), a seroresponse is defined as ≥4-fold rise from Day 1 (baseline) in anti-CHIKV SNA titer at Day 22.

Study Day 1 is defined as the day of IP administration on Day 1 (baseline). The day prior to Day 1 is Day -1. There is no Day 0. If the participant is not treated, then the Day 1 (baseline) is defined as the day of randomization.

Study day relative to Day 1 are calculated as:

- Study Day = (assessment date date of Day 1 + 1) if the assessment is on or after Day 1.
- **Study Day** = (assessment date date of Day 1) if the assessment is before Day 1.

For conversion of durations, 1 year = 365.25 days and 1 month = 365.25/12 = 30.4375 days.

Subgroups for sex (male and female), race (white and non-white) and ethnicity (Hispanic or Latino and Not Hispanic or Latino) are defined based on the corresponding demographic questions. Participants missing sex, race or ethnicity will be omitted from analyses by subgroup. Participants with "Not Reported" or Unknown" ethnicity are not included in ethnicity subgroups. Product lot subgroups are defined based on the lot variable in the randomization module dataset.

Summary statistics are described in Section 6.1.

Time duration (in days) between event A and event B is (date of event B – date of event A + 1). For conversion of durations, 1 year = 365.25 days and 1 month = 365.25/12 = 30.4375 days.

Treatment, actual, is defined as the treatment administered to the participant by the site (i.e., corresponding to the kit number used).

Treatment group is defined as PXVX0317 vaccine vs. placebo.

Treatment, randomized, is defined as the treatment assigned to the participant by the EDC (i.e., corresponding to the kit number assigned).

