5.9 Adverse Event Toxicity/Severity Grading

With the exception of redness and swelling, all solicited AEs are graded by the investigator according to severity grading scales from "mild" to "potentially life-threatening." The severity of redness and swelling, recorded as a diameter (mm) in the solicited adverse event diary, are summarized according to categories based on the largest-diameter linear measurement when a local reaction is present:

- Grade 0/absent = 0-24 mm.
- Grade 1/mild = 25-50 mm.
- Grade 2/moderate = 51-100 mm.
- Grade 3/severe = >100 mm.
- Grade 4/potentially life threatening = necrosis or exfoliative dermatitis.

Events reported as not present (0 mm is entered) are reported as Grade 0. Similarly, body temperatures recorded by the participant that are below 100.4° result in fever reported as Grade 0/absent.

Solicited AEs other than redness and swelling and unsolicited AEs are graded by the investigator for severity. The severity grading scales (Grade 1 = mild, Grade 2 = moderate, Grade 3 = severe, Grade 4 = potentially life-threatening) that are used for safety assessment in this study are provided in Appendix I of this document and Section 7.1.7 of the Protocol, based on the *FDA Guidance for Industry: Toxicity Grading Scale for Healthy Adult and Adolescent Volunteers Enrolled in Preventative Vaccine Clinical Trials* (2). Note that AEs that result in death are classified as Grade 4 and indicated as resulting in death.

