9.2.2.1 Electronic Diary Compliance

Participant compliance with e-diary or paper diary solicited adverse event entry are not summarized.

9.2.3 Unsolicited Adverse Events from Day 1 through Day 29

All unsolicited AEs occurring during the specified collection period in the study are recorded, regardless of their assessment of relatedness by the investigator. Unsolicited AEs include also those solicited AEs ongoing after seven days post-injection (Day 8), AESI, and SAEs.

All reported unsolicited AEs are summarized by treatment group according to MedDRA SOC, PT and highest reported severity. When an unsolicited AE occurs more than once for a participant, the maximum severity and closest relationship to treatment is counted. The unsolicited AE analysis includes unsolicited AEs judged by the investigator as at least possibly related to IP.

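### SAP 6.3 drops its worst-case assumption for a missing AE relationship or grade once another occurrence of the same AE exists, so a participant can fall to not related or below Grade 3

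*SAP*

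**What the plan says.** The rules stand in SAP 6.3, under the entries for related AEs and for AE severity. Each entry has two branches.

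- **Sole occurrence.** For causality, "if the relationship is missing for the only occurrence of an AE for a given participant, then that event is assumed to be related"; the sentence goes on to give conservatism as the reason. For severity, the entry ends "then that event is assumed to be severe in order to be conservative".
- **Other occurrences of the same AE exist.** For causality, the rule begins "If the relationship is missing for one or more occurrences of an AE for a given participant, the closest relationship of the remaining occurrences" and says that this value is used. For severity, "the maximum severity of the remaining occurrences of the AE for that participant is used".

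The grades are those of SAP 5.9: "Grade 1 = mild, Grade 2 = moderate, Grade 3 = severe, Grade 4 = potentially life-threatening". Protocol 7.1.8 and SAP 6.3 both count possibly and probably related events as related.

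For the participant-level tables of unsolicited AEs, SAP 9.2.3 says: "When an unsolicited AE occurs more than once for a participant, the maximum severity and closest relationship to treatment is counted". Protocol 8.7.2.2 has the same counting rule. SAP 6.5 adds no other rule for missing relatedness or severity and refers the reader back to 6.3.

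**The concern.** The two branches do not fit together. A participant with one event of unknown causality is counted as related. If the same participant also has a second occurrence of that AE, recorded as unrelated, the count changes to not related. The second occurrence says nothing certain about the first, whose causality is still unknown, yet it removes the worst-case assumption. The same happens with grade: an added mild or moderate occurrence lowers the participant's classification.

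Safety is a coprimary objective (protocol 2.2), and AE incidences are listed among the primary endpoints (protocol 8.3.1). They are described rather than tested, so the tables are themselves the safety result. The outputs that depend on these two attributes are the high-level summary (SAP 9.2.1) and the tables of related events and of Grade 3 or higher events in SAP Appendix I, for example 14.3.2.3, 14.3.2.4, 14.3.5.3 to 14.3.5.6, 14.3.5.8 and 14.3.5.12.

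**Working it through.** The plan states no figure here, so there is none to reproduce. The check is to run the rule over every possible pattern.

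**Inputs.** Relationship takes the values unrelated, possibly, probably (protocol 7.1.8). Grade takes the values 1 to 4 (SAP 5.9). The imputation branches are those of SAP 6.3, and collapsing takes the closest relationship and maximum severity (SAP 9.2.3). I take an occurrence of the same AE to mean the same term as tabulated.

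**Formula for grade.** Let m be the highest recorded grade among the other occurrences.

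- SAP rule: the missing grade is set to m, so the participant's maximum is max(m, m) = m.
- Worst case for each occurrence: the missing grade is set to 3, so the participant's maximum is max(3, m).
- Loss under the SAP rule: max(3, m) − m, which is 3 − m if m is below 3 and 0 otherwise.

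| Highest recorded grade m | SAP rule | Worst case per occurrence | Loss | SAP value for the missing event against sole-occurrence Grade 3 |
|---|---|---|---|---|
| 1 | 1 | 3 | 2 | lower |
| 2 | 2 | 3 | 1 | lower |
| 3 | 3 | 3 | 0 | same |
| 4 | 4 | 4 | 0 | higher |

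**Causality**, by the closest recorded relationship:

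| Closest recorded relationship | SAP rule | Worst case per occurrence |
|---|---|---|
| unrelated | not related | related |
| possibly | related | related |
| probably | related | related |

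The SAP rule therefore gives a lower class in 1 of 3 causality patterns and 2 of 4 grade patterns. These are counts of patterns, not probabilities.

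**Does participant-level counting repair it?** No. The maximum is taken after imputation, and the missing occurrence never receives the value related or Grade 3, so there is nothing for the maximum to pick up.

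**All attributes missing.** Suppose a participant has two occurrences and both lack a grade. Neither is the only occurrence, and no recorded occurrence remains to borrow from. Neither branch applies, so the result is undefined. The same holds for causality.

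**Unit of effect.** With the planned 2700 vaccinees as denominator, one reclassified participant is 1/2700 = 0.037%. The number of such participants cannot be computed, because the documents give no rate of missing relationship or grade.

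**The case against.** The two branches can be defended as a sensible order: use the participant's own worst recorded value first, and assume the worst only when nothing is recorded. The stated wish to be conservative is attached to the sole-occurrence branch, and borrowing the closest relationship and maximum severity resembles the participant-level counting rule. It is fair to say that the SAP does not promise worst-case imputation for every record. What stands against this is that the outcome moves the wrong way: adding an unrelated or milder occurrence lowers a participant's classification.

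The case will also be uncommon. The investigator must grade every AE and assess its causality (protocol 7.1.7, 7.1.8), and the data pass edit checks, queries and investigator sign-off (protocol 9.3). An affected participant needs a value still missing after that, a repeat of the same AE, and recorded values that are all unrelated or all below Grade 3. This stands, and it limits the weight of the point.

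A reader might infer that any second episode turns a missing event into an unrelated or mild one. The text does not support that: one related occurrence keeps the event related, one Grade 3 occurrence keeps it severe, and a Grade 4 occurrence puts it above the sole-occurrence value.

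A reader might also infer that the related-SAE results are materially understated. Nothing in the documents shows this. The rule does not stop a serious event from borrowing from a non-serious occurrence of the same AE, but SAEs are reported within 24 hours (protocol 7.3.1), the sponsor's medical monitor assesses their causality independently (protocol 7.1.8), and all are listed by participant (SAP 9.3.2).

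**Conclusion.** The point holds in a limited form. The SAP's worst-case assumption is withdrawn when another occurrence of the same AE exists. The participant is then counted lower than the missing event alone would have been if all recorded occurrences are unrelated (related becomes not related), or if all are below Grade 3 (a loss of one or two grades). Separately, the rule is silent when all of several occurrences lack the attribute.

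Understatement here means relative to the SAP's own worst-case assumption; the true relationship or grade is unknown. The same rule applies in both arms. Safety endpoints are reported for information only (protocol 8.6.2.5.2, SAP 6.4.2), so no hypothesis test or error rate is touched. This is a low-cost correction to the safety derivations and does not put the trial's conclusions in doubt.

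**What to change.** In SAP 6.3, replace the two-branch rules with one rule per attribute. Set each occurrence with a missing relationship to related, and each occurrence with missing severity to Grade 3, whatever the participant's other occurrences show. Then take the closest relationship and maximum severity per participant, as SAP 9.2.3 already does. Flag the imputed records in the AE listings (16.2.7.1 and 16.2.7.2.1).

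This never lowers a participant's classification compared with the current rule, and it settles the case in which all occurrences lack the attribute. It costs about two sentences in SAP 6.3 and a flag in the listings. The one drawback is that counts of related events and of Grade 3 or higher events may become slightly less favourable.

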3.3.10 Solicited Adverse Events

Solicited AEs will be collected from IP administration until Day 8. Solicited AEs for this study are local events of pain, redness, and swelling at the injection site and systemic events of oral temperature \geq 38.0°C (\geq 100.4°F), chills, fatigue, headache, myalgia, arthralgia, and nausea (Section 7.1.2 and Section 7.1.2.1).

Participants will be trained to complete an e-diary to observe, measure, and record these solicited AEs. In the occurrence of issues with the e-diary, a paper diary (subject memory aid) may be implemented as a back up. To measure oral temperature, a digital thermometer will be provided to the participant to measure their temperature each day and record them in their e-diary. To record injection site local reactions, a ruler will be provided to the participant to measure of redness and swelling at the largest point of the reaction each day. Adolescent participants will be instructed to complete the e-diary. Parents/guardians may provide assistance to adolescents to measure and record temperature and injection site reactions.

Study staff will review the signs and symptoms recorded in the e-diary. The investigator will then assess all solicited AEs for severity (Section 7.1.7) and the action taken, and causality (Section 7.1.8). The results of the investigator's assessment will be recorded as a separate source document and will be entered on the solicited AE eCRF. Symptoms continuing beyond the solicited AE collection period will be collected and recorded on the AE eCRF.

Details on definition, evaluation, reporting periods and documentation are outlined in Section 7.

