7.1.2 Solicited Adverse Event

A solicited AE is a protocol-specified AE about which the investigator (or designee) proactively asks the participants during a protocol-specified time period. A reactogenicity event may be considered as a solicited AE per discretion of the investigator (as described below in Section 7.1.2.1).

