8.3 Study Endpoints

8.3.1 Primary Endpoints

Safety Endpoints:

- Incidence of solicited AEs through Day 8 for PXVX0317 and placebo.
- Incidence of unsolicited AEs through Day 29 for PXVX0317 and placebo.
- Incidence of AESI, MAAEs and SAEs through Day 183 for PXVX0317 and placebo.

Coprimary Immunogenicity Endpoints:

• Difference in anti-CHIKV SNA seroresponse rate (PXVX0317 minus placebo) and associated 95% CI at Day 22.

Success criterion: Lower bound of the two-sided 95% CI on the difference in seroresponse rates between PXVX0317 and placebo groups (equivalent to a difference >0 using a two-sided chi-square test).

Note: Seroresponse rate (considered the presumptive seroprotection rate) is defined as the percentage of participants who achieve an anti-CHIKV SNA titer See Section 6.1 for assay description. See Section 8.6 for immunogenicity analysis details and Section 8.6.2.5 for success criteria and multiplicity controls.

• Anti-CHIKV SNA GMT and associated 95% CIs at Day 22 for PXVX0317 and placebo.

Success criterion: Significant difference in the IEP across all age groups combined using an ANOVA model with logarithmically transformed anti-CHIKV SNA titers (log₁₀) as the dependent variable and treatment group and study site as the fixed effects with a two-sided significance level of 0.05.

• Anti-CHIKV SNA GMT ratio between all three pairs of PXVX0317 lots (A:B, A:C, B:C) (adults 18 to <46 years of age) at Day 22.

Success criterion: Pairwise GMT ratios (A:B, A:C, B:C) each with a two-sided 95% CI within [0.667; 1.5] for the IEP in the 18 to <46 years of years of age stratum using an ANOVA model with log₁₀-transformed anti-CHIKV SNA titers as the dependent variable and vaccine lot and study site as the fixed effects to derive the GMT ratios.

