8.7.2.2 Unsolicited Adverse Events

All the unsolicited AEs occurring during the proscribed collection period in the study, will be recorded, regardless of their assessment of relatedness by the investigator.

The original verbatim terms used by investigators to identify AEs in the eCRFs will be mapped to PT using the MedDRA dictionary. The unsolicited AEs will then be grouped by MedDRA PT into frequency tables according to SOC. All reported AEs, as well as AEs judged by the investigator as at least possibly related to IP, will be summarized by treatment group, according to SOC and PT. When an unsolicited AE occurs more than once for a participant, the maximum severity and strongest relationship to the treatment group will be counted.

Only treatment-emergent AEs will be summarized (i.e., excluding those after a participant has given informed consent, but before vaccination).

Unsolicited AEs will be summarized by alphabetic SOC and preferred term as follows:

- Any unsolicited AE
- Related ("possibly" or "probably" related) unsolicited AEs
- Serious adverse events
- Related ("possibly" or "probably" related) SAEs
- Adverse events of special interest
- Medically-attended AEs
- Related MAAEs
- Unsolicited AEs leading to withdrawal
- Any AE leading to death

Listings of all AEs will be provided by participant.

Combined solicited and unsolicited AEs: Solicited AEs continuing beyond 7 days after vaccination will be coded by MedDRA and combined with the unsolicited AEs. A summary of participants with all combined solicited and unsolicited AEs, by SOC and PT, will also be provided.

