9.2.1 Overall Summary of Solicited and Unsolicited Adverse Events

A high-level summary of solicited and unsolicited AEs combined reviews the frequency counts and percentages of participants by treatment group reporting AEs in each of the following categories:

- Any AE and any AE \geq Grade 3
- Any solicited AE and any solicited AE \geq Grade 3

- Any treatment-related solicited AE and any treatment-related solicited AE \geq Grade 3
- Any unsolicited AE and any unsolicited AE \geq Grade 3
- Any SAE
- Any treatment-related SAE
- Any AE leading to study discontinuation
- Any fatal AE
- Any AESI (see definition in Section 6.3)
- Any MAAE and any treatment-related MAAE

In addition, summaries of combined solicited and unsolicited AEs by SOC, PT and highest reported severity are provided for the following populations:

- Safety population, all age groups
- Safety population by age strata
- Safety population by sex
- Safety population by race group
- Safety population by ethnicity
- Safety population by product lot

9.2.2 Solicited Adverse Events from Day 1 until Day 8

Solicited AEs recorded daily in the e-diary or paper diary until Day 8 include local (i.e., pain, redness, and swelling) and systemic reactions (i.e., fever, chills, fatigue, headache, myalgia, arthralgia, and nausea). In addition, solicited AEs ongoing after seven days post-injection (Day 8) and those that are serious or MAAEs are also recorded as unsolicited AEs. Severity of solicited AEs is assessed by the investigator in the same manner as unsolicited AEs.

Frequencies and percentages of participants experiencing each solicited AE are presented by maximum severity and by treatment group. The following summaries of solicited AEs are produced:

- Solicited AEs by maximum event severity, for each event and for any event
- Solicited AEs of severe (Grade 3) or higher severity, for each event and for any event
- Treatment-related solicited AEs by maximum event severity, for each event and for any event
- Day of first onset of solicited AEs, for each event and any event
- Duration of solicited AEs, for each event and any event
- Solicited AEs by day post-injection for each event and for any event

Occurrence of at least one AE by category (local, systemic) for solicited AEs are also included.

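### SAP 6.3 keeps a new, non-serious diary-recorded AE with onset on Day 9 or later out of the tables, although it falls inside the Day 29 unsolicited-AE endpoint

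*SAP*

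**What the plan says.** SAP 6.3 defines the solicited class by source: "AEs, solicited, are defined as those collected in the electronic e-diary or paper diary". The same entry notes that diary entry was meant to cover Days 1 to 8, and adds that "solicited AEs starting on Day 9 or later will be excluded from tabulations, with the exceptions of AESI and SAEs". The unsolicited class in SAP 6.3 is what remains: AEs held in the EDC that are not listed in the diary.

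The protocol defines the solicited class by period as well as by symptom: "A solicited AE is a protocol-specified AE about which the investigator (or designee) proactively asks the participants during a protocol-specified time period". Protocol 8.3.1 lists among the primary safety endpoints "Incidence of unsolicited AEs through Day 29 for PXVX0317 and placebo".

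Several rules move diary events into the unsolicited set:

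- Protocol 3.3.10: "Symptoms continuing beyond the solicited AE collection period will be collected and recorded on the AE eCRF".
- Protocol 8.7.2.2: "Solicited AEs continuing beyond 7 days after vaccination will be coded by MedDRA and combined with the unsolicited AEs". Protocol 7.1.2.1 says much the same.
- SAP 9.2.2: "solicited AEs ongoing after seven days post-injection (Day 8) and those that are serious or MAAEs are also recorded as unsolicited AEs".
- SAP 9.2.3: "Unsolicited AEs include also those solicited AEs ongoing after seven days post-injection (Day 8), AESI, and SAEs".

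**The concern.** Sorting by source in the SAP and by period in the protocol leaves a gap. An event that starts on Day 9 and is written in the diary is too late for the solicited tables. Because it is in the diary, it is also not unsolicited under the SAP definition. Each carry-over rule requires the reaction to have persisted past Day 8 or to meet a seriousness, AESI or attendance criterion.

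At stake is the completeness of a primary safety table. The rule can only lower the reported incidence, and two programmers could reasonably produce different tables from the same data.

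**Working it through.** There is no planned figure to reproduce; this is a reading of the rules, with some day counting.

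**Can such records exist?** Visit 3, when the diary is collected and reviewed, is Day 8 with a window of -1/+3 days: 8 - 1 = 7 to 8 + 3 = 11. A participant can therefore still hold the diary on Days 9 to 11. The SAP rule itself presupposes late entries.

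**Does the endpoint period cover them?** Unsolicited AEs are counted through Day 29. Days 9 to 29 are 29 - 9 + 1 = 21 days, all inside the period.

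**Where does one such event go?** Take a hypothetical mild arthralgia entered in the diary with onset on Day 9, gone by Day 10, with no medical visit. Arthralgia is a solicited symptom. It is an AESI only when medically attended (Protocol 7.1.4, SAP 6.3), so this event is neither AESI nor SAE nor MAAE.

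| Rule | What it admits | Admits this event? |
|---|---|---|
| SAP 6.3, solicited | Diary events; onset on Day 9 or later only if AESI or SAE | No |
| SAP 6.3, unsolicited | EDC events not listed in the diary | Not through the diary record |
| Protocol 3.3.10, 7.1.2.1, 8.7.2.2 | Reactions that continue past the diary period | No, it began afterwards |
| SAP 9.2.2 | Ongoing after Day 8, serious, or MAAE | No |
| SAP 9.2.3 | Ongoing after Day 8, AESI, or SAE | No |
| Protocol 7.1.3 and 7.2 | Spontaneously reported, or found by the investigator, and put on the AE eCRF | Only if the site makes that record |

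The last row is the only way in. It depends on the site, because Protocol 3.3.10 sends the investigator's assessment of diary events to the solicited AE eCRF.

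**Which tables?** The exclusion is not limited to the solicited tables, so as written it also reaches the combined solicited and unsolicited tables of SAP 9.2.1. If it were read as limited to the solicited tables, the event might appear in the combined tables, but the SAP definition would still keep it out of the unsolicited tables that serve the endpoint.

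**Weight of one participant.** The planned groups are 3 x 900 = 2700 vaccine and 450 placebo. One participant whose only unsolicited AE is such an event is worth 1/450 = 0.22 percentage points in placebo and 1/2700 = 0.04 in vaccine. This is a unit of scale only. The documents give no rate, so it does not say how many events are lost.

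**Two related mismatches.**

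- MAAEs: the solicited entry of SAP 6.3 and SAP 9.2.3 omit them from their lists. The unsolicited entry of SAP 6.3 and SAP 9.2.2 include them.
- Treatment emergence: SAP 6.5.2 treats every AE as treatment-emergent whatever its onset date. SAP 6.3, SAP 9.2 and Protocol 8.7.2.2 exclude AEs between consent and vaccination.

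**The case against.** The best defence is that the rule is sound housekeeping. Diary recording was planned only to Day 8 and the solicited endpoint runs only through Day 8, so keeping off-schedule entries out of the solicited tables is right. The rule acts on the diary record and does not delete an AE eCRF record of the same event. Unsolicited AEs are asked about at Visits 3, 4, 5 and 6, staff review the diary, and spontaneous reports go to the AE eCRF. A loss therefore needs both an off-schedule diary entry and no AE eCRF record from any of those four contacts.

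Most of this stands, and it limits the size of the point. It does not close the gap, because no text tells the site to open an AE eCRF record for a late diary onset, or the programmer to reclassify one. It might be said that an event starting on Day 9 is in a sense ongoing after Day 8. That does not fit the SAP, which sets these onsets apart for exclusion.

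Three stronger readings are tempting, and the documents do not support them:

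- *Every diary-type symptom starting on Days 9 to 29 is lost.* Wording in Protocol 3.3.11 and SAP 6.3 about AEs not listed in the diary could be read as excluding them by symptom type. But Protocol 7.1.2 ties solicited AEs to a period and Protocol 7.1.3 makes spontaneous reports unsolicited. A late symptom entered on the AE eCRF should count.
- *Medically attended events are lost.* SAP 6.3 defines an MAAE by an answer on the AE eCRF, so that record exists. SAP 9.2.2 sends it to the unsolicited set, and MAAE tables are planned.
- *Pre-dose events will be counted as treatment-emergent.* The SAP 6.5.2 sentence rests on AE collection starting on Day 1 and sits under a heading on missing or partial dates. Protocol 5.2.2 lists AE evaluation after dosing. No pre-dose AE record is shown to exist.

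**Conclusion.** The point holds in a narrow form and is minor. As written, the SAP leaves a new, non-serious, non-attended, diary-recorded AE with onset on Day 9 or later out of the tables unless a separate AE eCRF record is made, although onsets through Day 29 belong to a primary safety endpoint. That conclusion rests on the SAP wording being programmed literally and on some late diary entries lacking an AE eCRF counterpart. The documents do not show how often that happens; the number is probably small.

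Solicited incidence on Days 1 to 8 does not change, the participant listings retain the events, and no success criterion depends on them. A reader might infer a distorted vaccine-placebo comparison, but the documents give no rate by group from which to argue that. The MAAE and treatment-emergence mismatches are real in the text but have no shown effect on results.

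**What to change.** Before unblinding, amend SAP 6.3 so that diary events with onset on Day 9 or later stay out of the Day 1 to 8 solicited tables, but any event with onset on Days 9 to 29 is tabulated as unsolicited, whatever its symptom type or source form. Count it once if it is in both the diary and the AE eCRF, and refer to Protocol 7.1.2 and 7.1.3 for the definitions.

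In the same edit, name MAAEs in the solicited entry of SAP 6.3 and in SAP 9.2.3, to match the unsolicited entry of SAP 6.3 and SAP 9.2.2. Limit the SAP 6.5.2 sentence to AEs whose onset date is missing or partial and cannot be shown to precede IP administration, so that it agrees with SAP 6.3, SAP 9.2 and Protocol 8.7.2.2.

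The cost is a few sentences, one derivation flag, and MedDRA coding of any late diary entries. No new data are needed. Unsolicited AE percentages may rise slightly.
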